## LIST OF ABBREVIATIONS

ABR	Auditory Brainstem Response
Lf	Oral Lactoferrin
BMI	Body Mass Index
COI	Conflict of Interest
CRP	C-reactive Protein
CV	Coefficient of Variation
DHA	Docosahexaenoic Acid
DHHS	Department of Health and Human Services
DMC	Data Monitoring Committee
DSMB	Data and Safety Monitoring Board
DSMP	Data and Safety Monitoring Plan
EPO	Erythropoietin
EMR	Electronic Medical Record
Fe	Iron
FERPA	Family Educational Rights and Privacy Act
FDA	Food and Drug Administration
GCP	Good Clinical Practice
Hg	Hemoglobin
HIPAA	Health Insurance Portability and Accountability Act
IBC	Institutional Biosafety Committee
ICD	Informed Consent Document
ICH	International Conference of Harmonization
ID	Iron Deficiency
IDA	Iron Deficiency Anemia
IDE	Investigational Device Exemption
IDS	Investigational Drug Service
IL-6	Interleukin-6
IND	Investigational New Drug
IRB	Institutional Review Board
LAR	Legally Authorized Representative
LD	Labor and Delivery
OHRP	Office of Human Research Protections
OPRS	Office for the Protection of Research Subjects
PHI	Protected Health Information
PI	Principal Investigator
PNV	Prenatal Vitamin
PPRA	Protection of Pupil Rights Amendment
QA/QI	Quality Assurance/Quality Improvement
SAE	Serious Adverse Event
SOP	Standard Operating Procedure
UIC	University of Illinois at Chicago
WG	Weeks Gestation

## 1.0 Project Summary/Abstract

*Maternal iron deficiency anemia (IDA) increases the risk of adverse pregnancy outcomes and can negatively impact the iron endowment of the neonate that may cause irreversible deleterious effects on neurodevelopment. To avert IDA in pregnancy, women are universally prescribed a daily oral supplement containing ~27 mg of iron. However, there is growing concern regarding the efficacy of this one-size-fits-all approach for women with systemic inflammation, including women with obesity. Obese women experience disruption to the hepcidin-ferroportin complex deeming iron from diet, including supplemental iron, and body stores less bioavailable. This indicates an urgent need to develop and test new methods to prevent maternal IDA among women with obesity. In this planning grant application, we will develop the clinical and research infrastructure to test the preliminary efficacy of oral lactoferrin (Lf) supplementation for the prevention of maternal IDA among obese women. Lactoferrin is a natural compound found in secretions from mammals, including milk, and is an important regulator of body iron balance given its effects on inflammation and the hepcidin-ferroportin complex. Daily oral Lf has been shown to be superior to oral iron supplementation for treating IDA in pregnant women with inflammation but has not been studied for its ability to prevent IDA in pregnancy. The specific aims of this clinical trial planning grant include: 1) Conduct provider facing one-on-one interviews to inform and optimize a clinical research intervention into the clinical infrastructure at the Center for Women's Health at UIC and, 2) Pilot test a randomized controlled trial of oral Lf supplementation from early second trimester up through delivery among 40 pregnant women with obesity at risk of IDA. In this aim we seek to understand recruitment, adherence, and retention rates and intervention acceptability to determine feasibility and preliminary efficacy on maternal inflammation and maternal and neonatal iron and hematological-related markers. This study will provide first of its kind data, necessary and sufficient to inform and develop a large-scale efficacy trial of oral Lf as a safe and scalable natural compound for the prevention of IDA among obese women. Ultimately if successful, this project is an important first step toward improving prenatal care for obese women who represent more than a third of reproductive-age women in the United States.*

## 2.0 Background/Scientific Rationale

*Iron is essential for all cells and is particularly vital in pregnancy for the growth and maintenance of the placenta, expansion of the maternal red blood cell mass, fetal growth and neurocognitive development, and the neonatal iron endowment that supports ex utero brain development. Conversely, decreases in maternal iron status that lead to IDA increase the risk of maternal and infant mortality, spontaneous preterm birth, and enduring neurocognitive defects in infants. Recent animal and human data indicate that maternal IDA and reduced maternal iron bioavailability is associated with poor infant iron status at birth, posing a significant threat to neurocognitive development. In an effort to optimize iron status and avert IDA in pregnancy, U.S. women are universally prescribed a daily oral prenatal supplement containing ~27 mg of iron as a ferric or ferrous iron salt. However, there is growing concern regarding the efficacy of this one-size-fits-all approach given the discovery of the hepcidin-ferroportin complex and its role in systemic iron regulation.*

*In pregnancy, a woman's dietary iron absorption efficiency is enhanced, a compensatory mechanism to fulfill maternal iron needs and increased placental iron uptake and iron flux to the fetus as the pregnancy progresses. It is believed this mechanism is largely supported by the suppression of maternal hepcidin, a liver-derived peptide hormone and master regulator of systemic iron homeostasis. Hepcidin controls systemic iron metabolism through its regulation of the ferroportin iron exporter. Hepcidin promotes ferroportin's degradation thereby reducing the efflux of iron from intestinal enterocytes, reticuloendothelial macrophages, and hepatocytes. Hepcidin is simultaneously regulated by iron stores, erythropoiesis and systemic inflammation. In persons with systemic inflammation, hepcidin production is enhanced, resulting in diminished ferroportin expression and reduced iron export into circulation from diet and stores. This phenotype, commonly referred to as the anemia of inflammation, is associated with iron delocalization specifically normal to elevated ferritin (i.e., iron trapping), low hematological parameters [e.g., hemoglobin (Hb)], and systemic inflammation [e.g., elevated interleukin-6 (IL-6)]. Importantly, supplementing with oral iron salts (e.g., ferrous sulfate) in persons with underlying systemic inflammation has limited efficacy for preventing or treating IDA because hepcidin is a negative regulator of dietary iron absorption.*

*There is increasing evidence that hepcidin can be overexpressed in pregnant women with obesity. Pre-pregnancy obesity, a condition affecting 36% of reproductive age women in the U.S., is often accompanied by chronic systemic inflammation and is a risk factor for neonatal ID. In 2014, a small case control study reported that women with pre-pregnancy obesity (n = 20) had higher systemic inflammation and hepcidin in the second trimester and at the time of delivery compared to lean women (n = 20, BMI 18.5 - 24.9 kg/m^2). Moreover, the neonates birthed by the obese women had lower cord iron status compared to the neonates born to the lean women. In a separate case-control study, maternal obesity was associated with impaired neonatal cord iron status at delivery compared to neonates birthed by lean women. Specifically, neonatal tissue iron stores were compromised to support Hb, a partitioning that may have a profound*

effect on growth and neurodevelopment. Several other research teams have examined links between maternal obesity and maternal-fetal iron regulation in large observational cohorts, with findings garnering mixed results. The lack of consistency among the various studies may be related to the degree of adiposity of the women investigated. For example, one study stratified by extreme obesity (BMI  $\geq 35.0$  kg/m^2) found that serum hepcidin was 50% higher in the 2nd trimester and at the time of delivery among severely obese women (but not among overweight or class I obese women) compared to women that were lean, indicating that a certain BMI threshold may be necessary to skew iron homeostasis in pregnancy. In our preliminary data, described in detail below, pregnant women with pre-pregnancy obesity (mean BMI  $35.3 \pm 5.0$  kg/m^2) had greater systemic inflammation, overexpressed hepcidin, lower dietary iron uptake and less iron transferred to their fetus. Our findings are important given we used a stable iron isotope to objectively trace iron from maternal uptake to neonatal cord blood – no other studies to date have used this rigorous approach to examine iron homeostasis in obese pregnancy. Our findings indicate that the flow of iron from mother to fetus is impaired in women with pre-pregnancy obesity. Moreover, our preliminary data suggest that the current universal approach to prevent IDA in pregnant women with obesity, a daily oral prenatal supplement containing iron, is suboptimal given their underlying inflammatory status. This is a call to action given that disturbances to maternal iron homeostasis can result in irreversible, lifelong adverse health effects in infants, coupled with the high rate of obesity among reproductive age women in the U.S. Clearly, alternatives to preventing maternal IDA are needed for pregnancies complicated by obesity.

Lactoferrin (Lf) is an iron binding glycoprotein secreted by exocrine glands and neutrophils that is present in mammalian biological fluids including milk, saliva, tears, and cervical mucus. Lf is involved in both iron homeostasis and inflammation and is closely related to the iron transport protein transferrin although it can retain iron at a lower pH. Of relevance to the proposed trial is evidence that Lf can suppress the production and release of pro-inflammatory cytokines including IL-6. This mechanism of action is important given IL-6 modulates hepcidin (i.e., promotes its upregulation) which leads to reduced ferroportin activity. In a trial conducted in pregnant women with concurrent hereditary thrombophilia, IDA, and underlying systemic inflammation, led by our team member [name], oral supplementation with bovine-derived Lf (Lf) (which has similar structure to human Lf and can bind to human Lf receptors to exert biological activity) led to large reductions in circulating IL-6 and clinically significant improvement in iron and hematological parameters, compared to standard oral iron salt supplementation (330mg ferrous sulfate). Importantly this effect was observed in the absence of additional oral supplemental iron. Oral Lf is thought to improve body iron balance by enhancing ferroportin-mediated iron export by limiting inflammation and decreasing blood levels of both IL-6 and hepcidin — ultimately increasing iron bioavailability in the absence of additional direct iron supplementation. Moreover, in pregnant women with IDA, daily oral Lf when tested against standard oral ferrous sulfate and ferrous fumarate supplementation was superior for improving Hb and was associated with significantly fewer adverse side-effects (i.e., gastrointestinal disturbances) and enhanced acceptability. To our knowledge, there exists no clinical

*data to show the effectiveness of oral Lf supplementation for preventing IDA among pregnant women with obesity, despite a biological pretense for why oral Lf may be beneficial in this context. In summary, oral Lf is a safe compound to counteract inflammation, regulate the hepcidin-ferroportin axis and rebalance iron homeostasis in the absence of additional oral iron in a way that may be uniquely beneficial for preventing IDA among pregnant women with obesity given their underlying inflammatory status.*

*Effects of oral Lf vs. oral iron on iron homeostasis among women with hematologic disorders and complicated pregnancies. Our team member, professor [name] recently published a study examining the efficacy of twice daily (100mg/dose) oral Lf vs. once daily oral iron supplementation (330mg ferrous sulfate) for the treatment of concurrent anemia of inflammation and IDA in pregnant women with the hereditary hematologic disorder thrombophilia. Women with anemia of inflammation/IDA have a similar phenotype, albeit more extreme, to what is observed in obesity, i.e., systemic inflammation, overexpressed hepcidin, elevated body iron stores (ferritin) and decreased Hb. [name] found that after 30 days of supplementation and at the time of delivery, oral Lf was associated with a significant reduction in IL-6 and hepcidin and statistically and clinically significant improvements in iron and hematological parameters (Table 1). Notably there were no changes in the women receiving oral ferrous sulfate. Also noteworthy is the fact that there were no adverse effects on the fetus/neonate (e.g., amniotic fluid index or birth outcomes) with either intervention. An exploratory analysis examining the impact of daily oral Lf on iron and hematological parameters in pregnant women with insulin resistance (n = 3) showed that after 30 days of supplementation, there was an increase from baseline in Hb ( $10.4 \pm 0.3$  to  $11.4 \pm 0.3$  g/dL) and serum iron ( $33 \pm 2$  to  $56 \pm 11$   $\mu\text{g/dL}$ ). This data is particularly intriguing given pregnant women with insulin resistance most closely represent the metabolic phenotype observed in obesity. Together, the data suggest that oral Lf supplementation safely elicits an anti-inflammatory effect that modulates the hepcidin-ferroportin complex to improve maternal iron homeostasis. This trial provides strong evidence that oral Lf supplementation, in the absence of additional oral iron, could be used to safely optimize iron homeostasis and prevent IDA in women with obesity.*

**Table 1. Hematological, iron, IL-6 and hepcidin mean values  $\pm$  SD of pregnant women with hereditary thrombophilia and anemia of inflammation treated with oral bLf or ferrous sulfate baseline, after 30 days of treatment, and at delivery**

	Oral bLf (n=40)			Oral ferrous sulfate (n=25)		
	Baseline	After 30 days	Delivery	Baseline	After 30 days	Delivery
Red blood cells x 10 	3,750 $\pm$ 127	4,354 $\pm$ 198*	4,482 $\pm$ 147*	3,650 $\pm$ 163	3,960 $\pm$ 230	4,029 $\pm$ 287
Hb, g/dL	10.6 $\pm$ 0.4	12.2 $\pm$ 0.4*	12.7 $\pm$ 0.5*	10.8 $\pm$ 0.8	11.3 $\pm$ 1.1	11.2 $\pm$ 0.9
Serum iron, $\mu$ g/dL	36 $\pm$ 11	63 $\pm$ 9*	85 $\pm$ 10*	40 $\pm$ 15	40 $\pm$ 6	38 $\pm$ 11
Serum ferritin, ng/mL	11 $\pm$ 6	18 $\pm$ 2	31 $\pm$ 3*	17 $\pm$ 14	14 $\pm$ 9	12 $\pm$ 10
Serum IL-6, pg/mL	89 $\pm$ 8	58 $\pm$ 6*	50 $\pm$ 5*	85 $\pm$ 12	108 $\pm$ 7	113 $\pm$ 15
Serum hepcidin, ng/mL	115 $\pm$ 23	65 $\pm$ 10*	54 $\pm$ 13*	107 $\pm$ 29	112 $\pm$ 32	116 $\pm$ 26

\*significantly different from baseline, p < 0.001

### 3.0 Objectives/Aims

**Aim 1: Conduct provider interviews to gauge best practices for integrating clinical research and patient recruitment into the Center for Women’s Health clinical workflow.** We will recruit 9-12 providers from the Physician attending/Physician resident, nurse-midwife and nurse positions to complete a 30-60-minute one-on-one interview and 5-minute electronic demographics survey.

**Aim 2: Pilot test a randomized controlled trial of oral Lf supplementation among pregnant women with pre-pregnancy obesity at risk of IDA.** We will randomize 40 women to once-daily oral Lf (250mg) or usual care from early second trimester through delivery to: **a)** Understand recruitment, adherence, and retention rates and intervention acceptability to determine feasibility; and **b)** Determine preliminary efficacy on maternal inflammation and maternal and neonatal iron and hematological markers.

### 4.0 Eligibility

**Aim 1:** We will recruit physician attendings, physician residents, nurse-midwives and nurses from the Center for Women’s Health at UIC (9-12 individuals in total). The only eligibility is to be a current provider at the Center for Women’s Health.

**Aim 2:** We will recruit 60 women to enroll 40 women and obtain a final sample of 32 women (16/arm). Women will be referred by their provider to the study team and recruited following their initial new OB visit either in-person at an upcoming clinical visit or by phone to determine interest and confirm eligibility. Women will also be identified and pre-screened by study staff through provider scheduling records and patient EMR to assess provider referral rates. We have found in our previous studies that waiting

*until after the new OB visit is completed streamlines the recruitment process substantially, since the initial visit yields a detailed History and Physical, estimated dating of gestational age, and new OB clinical labs. Interested and eligible women will be invited to schedule a baseline research visit.*

#### **4.1 Inclusion Criteria**

##### **Aim 1:**

- *current physician, nurse-midwife or nurse in the Center for Women's Health at UIC*

##### **Aim 2:**

- *single*
- *naturally conceived pregnancy*
- *at risk of IDA [Hb 11.0 – 12.9 g/dL (first trimester)/10.5 – 12.5 g/dL (second trimester)] based on new OB complete blood count (CBC) results obtained from the EMR*
- *18 – 45 years old*
- *pre-conception BMI  $\geq$  28.0 kg/m^2 [based on measured height in EMR and recent pre-conception weight (within 3 months of pregnancy) from EMR if available or self-reported]; < 24 WG*
- *fluency in English to provide consent and complete study procedures*
- *ability to provide consent*
- *and ownership of a smartphone (currently more than 90% of our patient population at the Center for Women's Health)*
- *For ABR testing, the infant must have a normal hearing screen recorded in the electronic medical record (EMR). This is a requirement for normal ABR testing protocol.*

#### **4.2 Exclusion Criteria**

##### **Aim 1:**

- *None*

##### **Aim 2**

- *IDA requiring high dose supplemental iron*
- *allergy to milk proteins or wheat*
- *vegan (due to content of the supplements)*
- *recent blood transfusion*
- *previously diagnosed type 1 or type 2 diabetes*
- *autoimmune disorder (e.g., rheumatoid arthritis)*
- *inflammatory bowel disease*

- *current bacterial or viral infection*
- *history of bariatric surgery*
- *malabsorptive disease*
- *current hyperemesis*
- *current eating disorder*
- *hematologic disorder or trait carrier (e.g., hemochromatosis,  $\beta$ -thalassemia)*
- *current tobacco, alcohol or illicit drug use (not including marijuana)*
- *and regular use of medications that may interfere with nutrient absorption*
- *We have also found in our previous studies a recent traumatic event (e.g., death of a significant other or parent) may make it difficult to comply with the interventions, hence these women will also be excluded.*
- *First trimester Patient Health Questionnaire depression screener (PHQ-8) >10 is indicative of moderate to severe depressive symptoms and in our previous studies women with a score PHQ-8 >10 had difficulty complying with study measures. Women with a score >10 from the initial prenatal visit in the EMR, or if one is not available in the EMR, at screening will be excluded for study participation. The participant's provider will be notified via EPIC in basket message flagged as high priority and a member of the research team will monitor whether the provider read the message from the study team. If the participant is found to have a score >10 in the preliminary screening of the EMR, they will not be approached for recruitment.*

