**Study Arms.** Women will be randomly assigned (3:1) to one of the two study arms described below. Women will not be blinded to their treatment assignment. Women will receive a month's worth of supplements at a time. Refills will occur at monthly research visits that are coordinated with clinical care. Based on our current probiotic supplementation trial, women receive between 5-6 refills over the course of their pregnancy depending on the timing of their study entry. We have opted to test once daily Lf (250mg) versus a lower dose (100mg) taken twice daily (as was used by our team member [name] in her previous trial) due to the common availability of Lf formulations in the U.S. commercial market, as well as the logistics around once vs. twice daily supplementation in our patient population. The supplements will be dispensed in bottles by the UIC Investigational Drug Service.

**Once daily Oral Lf (250mg).** Women assigned to this group will be instructed to consume an oral Lf capsule one hour prior to their afternoon meal and two prenatal vitamin/mineral supplement gummies without iron with omega-3 fatty acids before bed from early second trimester (15 - 24 WG) up through delivery. Women are advised to consume the Lf prior to meals, given our team member [name]'s unpublished work shows its superior efficacy for improving iron and hematological parameters among pregnant women with hereditary thrombophilia versus when consumed with meals. The 250mg Lf capsule will be sourced from Jarrow Formulas (Los Angeles, CA. The supplement (**Fig. 2**), available commercially, has been previously tested in pregnancy and includes 250mg Lf in addition to cellulose, magnesium stearate (vegetable source), silicon dioxide, and gelatin capsule material. Jarrow sources their Lf from Glanbia Nutritionals (Chicago, Illinois). Per the manufacturer, the Lf is approximately 14.3% saturated with iron or contains 17.6 mg/100g; we will confirm this with our own purity testing as described below. The prenatal vitamin/mineral gummies will be a commercially available product (OLLY The Essential Prenatal Multi). The nutritional content of the prenatal gummies is presented in **Fig. 3**. Women in both groups will be advised to consume an iron-rich diet and provided a handout detailing foods rich in heme and non-heme iron.

Figure 2. Jarrow Formulas Oral Lactoferrin supplement Facts Label

Supplement Facts		
Serving Size 1 Capsule		
Servings Per Container 60		

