Amount Per Serving	% DV	
Lactoferrin (Apolactoferrin)	250 mg	†
† Daily Value not established.		

Figure 3. OLLY The Essential Prenatal Multi, Supplement Facts

Supplement Facts			
Serving Size 2 Gummies			
Servings Per Container 30			
Amount Per Serving	% DV for Pregnant & Lactating Women	Amount Per Serving	% DV for Pregnant & Lactating Women
Calories	30	Folate	667 mcg DFE 111% (400 mcg folic acid)
Total Carbohydrate	6 g 2%†	Vitamin B12 (as cyanocobalamin)	8 mcg 286%
Total Sugars	4 g **	Choline (as choline bitartrate)	10 mg 2%
Includes 4g Added Sugars	8%†	Zinc (as zinc sulfate)	3.8 mg 29%
Protein	less than 1 g	Sodium	5 mg <1%
Vitamin A (as retinyl palmitate)	1200 mcg 92%	Omega-3s (from fish oil)	70 mg **
Vitamin C (as ascorbic acid)	30 mg 25%	DHA (docosahexaenoic acid)	50 mg **
Vitamin D (as cholecalciferol)	10 mcg (400 IU) 67%	EPA (eicosapentaenoic acid)	10 mg **
Vitamin E (as dl-alpha tocopheryl acetate)	6.8 mg 36%	Other Omega-3s	10 mg **
Niacin (as niacinamide)	20 mg 111%		
Vitamin B6 (as pyridoxine hydrochloride)	2.5 mg 125%		
†Percent Daily Values (DV) are based on a 2,000 calorie diet.			
**Daily Value (DV) not established.			

*Usual Care (Control). Women assigned to this group will be instructed to consume a commercially available prenatal vitamin/mineral supplement with iron and omega-3 fatty acids (Prenatal 1, Bayer Healthcare, Whippany, NJ) before bed from early second trimester (15-24 WG) through delivery. To minimize variability in prenatal vitamin/supplement use across the participants, we have opted to standardize the prenatal vitamin/mineral supplement by providing women in the usual care arm a supplement that is nutritionally like what is prescribed by the Center for Women’s Health providers. The nutritional content of the study-provided prenatal vitamin/mineral supplement is presented in Fig. 4. Women will be advised to consume an iron-rich diet and provided a handout describing foods rich in heme and non-heme iron.*

Figure 4. Prenatal-1, Bayer Healthcare, Supplement Facts

Supplement Facts		
Serving Size: One softgel		
	Amount Per Serving	% Daily Value for Pregnant and Lactating Women
Calories	5	
Calories From Fat	5	
Total Fat	0.5 g	*
Polyunsaturated Fat	0.5 g	*
Cholesterol	25 mg	*
Total Carbohydrate	0 g	*
Sugars	0 g	*
Vitamin A (50% as beta-carotene)	4000 IU	50%
Vitamin C	60 mg	100%
Vitamin D	400 IU	100%
Vitamin E	30 IU	100%
Thiamin (B 1 )	1.7 mg	100%
Riboflavin (B 2 )	2 mg	100%
Niacin	20 mg	100%

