Vitamin B 6	2.5 mg	100%
Folic Acid	800 mcg	100%
Vitamin B 12	8 mcg	100%
Biotin	300 mcg	100%
Pantothenic Acid	10 mg	100%
Calcium	200 mg	15%
Iron	28 mg	156%
Iodine	150 mcg	100%
Magnesium	50 mg	11%
Zinc	15 mg	100%
Copper	2 mg	100%
Omega-3 Fatty Acids (from fish oil)	235 mg	*
DHA (docosahexaenoic acid)	200 mg	*
EPA (eicosapentaenoic acid)	35 mg	*

*Purity Testing of Oral Lf Capsules. Purity testing of the Lf capsules will be conducted using SDS-PAGE and silver nitrate staining, concentration via UV spectroscopy, iron saturation via spectroscopy and lipopolysaccharide contamination by Limulus Amebocyte Lysate assay (Sigma Aldrich, St. Louis, MO). Lf purchased from Sigma Aldrich will serve as the reference standard (St. Louis, MO). All purity testing will be conducted by Avomeen Analytical Services (Ann Arbor, MI).*

*Study Feasibility. We will collect detailed records of the number of women eligible and then referred by Center for Women’s Health clinical staff to the research team. We will also track the number of referred women approached (by phone & in person) by our research team for enrollment and the number of women who decline and their reasons for non-enrollment. Once a woman is enrolled in the study, attendance at study visits, completeness of data, and overall and treatment specific loss to follow-up/withdrawal will be closely monitored. To track progress of subjects through the trial, we will adhere*

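### The content-based exclusions in Section 4.2 do not address fish, although the prenatal products supplied in both arms list fish oil

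*Combined protocol and SAP*

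**What the plan says.** The Aim 2 exclusion list in Section 4.2 contains two entries that depend on what is in the supplements. One is "allergy to milk proteins or wheat", which is the only allergy named. The other is "vegan (due to content of the supplements"), which gives product content as its reason.

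Section 6.0 (Study Arms) describes three supplied products:

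- **Lactoferrin capsule (lactoferrin arm).** The inactive ingredients include "silicon dioxide, and gelatin capsule material".
- **Prenatal gummies (lactoferrin arm).** These women are told to take "two prenatal vitamin/mineral supplement gummies without iron with omega-3 fatty acids before bed". The label in Figure 3 reads "Omega-3s (from fish oil"), 70 mg per two-gummy serving.
- **Prenatal softgel (usual care).** These women receive a "commercially available prenatal vitamin/mineral supplement with iron and omega-3 fatty acids". The label in Figure 4 reads "Omega-3 Fatty Acids (from fish oil"), 235 mg per softgel.

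On assignment, the plan states: "Women will be randomly assigned (3:1) to one of the two study arms described below". No third arm and no alternative prenatal product is described.

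**The concern.** The exclusion list is evidently meant to keep out women who should not, or would not, take what the trial supplies. An ingredient printed on both prenatal labels is missing from it. Screening staff who apply the list exactly as written have no prompt to ask about fish allergy. Because fish oil is in both arms, randomisation cannot steer such a woman away from it.

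This is first a matter of participant safety, in a population that Section 4.3 itself calls vulnerable. The safeguards that Section 7.0 describes for reactions to the intervention are symptom reports by text, follow-up calls and discontinuation. All of them act after exposure has begun, whereas a screening question acts before it.

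**Working it through.** The plan states no figure on this point, so there is nothing to reproduce. The check has three parts.

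**1. Criteria against labels**

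| Content | Where it is printed | Arm | Addressed in Section 4.2? |
|---|---|---|---|
| Fish oil, 70 mg omega-3 (50 + 10 + 10) | Figure 3 | Lactoferrin | Not named; only vegans excluded |
| Fish oil, 235 mg omega-3 (200 + 35) | Figure 4 | Usual care | Not named; only vegans excluded |
| Gelatin | Capsule description, Section 6.0 | Lactoferrin | Not named; only vegans excluded |

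The component lines add up to the omega-3 totals on both labels, so the fish-oil entries are legible and consistent. Arms whose prenatal product contains fish oil: 2 of 2. Neither the inclusion criteria in Section 4.1 nor Section 4.3 mentions fish. The vegan exclusion does not close the gap, because a woman with fish allergy who eats meat, eggs or dairy is not vegan.

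**2. Length of possible exposure**

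Entry is at 15 to 24 weeks' gestation and supplements continue to delivery (Section 6.0). Delivery at 40 weeks is an assumption.

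- Entry at 15 weeks: (40 − 15) × 7 = 175 days.
- Entry at 24 weeks: (40 − 24) × 7 = 112 days.

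**3. Chance that the situation arises**

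Only randomised women receive product, so n = 40. The prevalence p of fish allergy is not in the documents and is varied here as an assumption. Women are treated as independent, and it is assumed that nothing outside the written criteria screens such a woman out.

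P(at least one) = 1 − (1 − p)^40

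| Assumed p | Calculation | Result |
|---|---|---|
| 0.2% | 1 − 0.998^40 | about 8% (7.7%) |
| 0.5% | 1 − 0.995^40 | about 18% |
| 1% | 1 − 0.99^40 | about 33% |
| 2% | 1 − 0.98^40 | about 55% |

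These probabilities do not depend on the allocation ratio, because both arms supply fish oil.

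**The case against.** The best case for leaving the text alone has four parts.

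- **Harm is not shown.** A reader might infer that a woman with fish allergy would react to these products. The documents do not say whether the oil carries allergenic protein, so this does not follow. This part stands: what is established is the gap in the criteria, not a clinical consequence.
- **Other steps might catch her.** Recruitment follows a new obstetric visit with a detailed history, the Investigational Drug Service dispenses, and health status is checked weekly. The consent pages are not in the copy available, so ingredients may be disclosed there. This makes it wrong to say that such a woman would certainly be enrolled; she could be. But none of these steps is a written check of allergies against the labels.
- **The likelihood is easily overstated.** Using the 60 women to be recruited would give 11% to 70% over the same assumed prevalences. Those 60 are approached in order to enrol 40, and only the 40 are given product.
- **No analysis is affected.** Fish oil is in both arms, and no estimand or model changes. This also stands, and it limits the weight of the point.

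Three further inferences are tempting, and the documents do not support them.

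- *The wheat exclusion is unjustified because no label shows wheat.* Figures 3 and 4, as supplied, are nutrient panels without a full ingredient list or allergen statement, so the absence of wheat from them shows nothing.
- *Section 7.0 relies on a fish-related exclusion when it mentions women with contraindications.* That sentence is in the item on adverse effects of oral lactoferrin and does not concern the prenatal products. For the same reason it does not fill the gap.
- *Vegetarians, or women who avoid fish or gelatin on religious grounds, will enrol and then be counted as non-adherent.* Participation is voluntary and unblinded, and nothing in the documents indicates how many such women would join and then stop.

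**Conclusion.** The mismatch is real. Section 4.2 sets exclusions by product content, both prenatal labels list fish oil, only two arms exist, and no listed criterion addresses fish. Read literally, the criteria admit a woman with fish allergy and could give her a fish-oil product daily for about 112 to 175 days, whichever arm she draws.

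Confidence in the textual gap is high. The size of the risk cannot be judged from the documents. The 8% to 55% range describes the chance of at least one such woman among 40 under assumed prevalences of 0.2% to 2%. It is not an estimate for this trial and says nothing about the chance of a reaction. The gap should still be closed, because the plan's own eligibility logic does not match its printed product content and the correction is cheap.

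**What to change.** Reconcile the allergy and content-based exclusions in Section 4.2 with the full ingredient and allergen labels of all three supplied products: the lactoferrin capsule, the prenatal gummies and the prenatal softgel. State explicitly how fish content, and gelatin content, is handled at eligibility, and add one matching question to the screening form. If the sponsor holds evidence that the fish oil in these products is not a concern for women with fish allergy, it can be recorded at the same place. The clinical rule itself is for the sponsor and the medical oversight physician to decide.

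The cost is about one line in Section 4.2 and one screening question. The downside is that a very few otherwise eligible women might be excluded.
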